### **Study Treatments:**

A0081106 study medication will be provided as pregabalin liquid oral solution or oral capsules. Subjects <4 years of age at Visit 1 or who are enrolling from A0081042 will receive study medication 3 times daily (TID) in equally divided doses. Subjects who are  $\geq 4$  years of age at Visit 1 will receive study medication twice daily (BID) in equally divided doses.

- All eligible pediatric subjects 1 month to 16 years and 11 months of age will take pregabalin in Study A0081106 at a dosage according to their body weight:
  - Pediatric subjects weighing  $\geq 30$  kg will begin pregabalin dosing at 2.5 mg/kg/day (maximum 150 mg/day). Subjects will remain at the starting dose for 8 days until Visit 2. Thereafter, dosing will be flexible based on individual seizure response and tolerability. Pediatric subjects may have their dose adjusted up or down at clinic visits in increments of no more than 2.5 mg/kg/day (maximum 150 mg/day) to daily dose levels of 5.0 (maximum 300 mg/day), 7.5 (maximum 450 mg/day), or 10.0 mg/kg/day (maximum 600 mg/day).
  - Pediatric subjects with body weight <30 kg will begin pregabalin dosing at 3.5 mg/kg/day until Visit 2. Thereafter, dosing will be flexible based on individual seizure response and tolerability. Pediatric subjects may have their dose adjusted up or down at clinic visits in increments of no more than 3.5 mg/kg/day to daily dose levels of 7.0, 10.5, or 14.0 mg/kg/day. This 40% higher dose per kg in pediatric subjects with body weight <30 kg is needed to achieve exposures similar to those of adults or pediatric subjects weighing  $\geq 30$  kg.
- All eligible adult subjects 17 to 65 years of age will begin dosing of pregabalin in Study A0081106 at the level of 150 mg/day. Subjects will remain at this dose for 8 days until Visit 2. Thereafter, dosing will be flexible based on individual seizure response and tolerability. Adult subjects may have their dose adjusted up or down at

clinic visits in increments of no more than 150 mg/day to dose levels of 300, 450, or 600 mg/day.

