b. If procedures were performed during participation in Studies A0081041, A0081042, or A0081105 the actual procedure will not need to be repeated for the Study A0081106 Screening Visit 1A (data from the subject's previous study will be utilized).

- For at-risk subjects, a mental health risk assessment must be performed by a qualified mental health professional.

c. Female subjects who are menarchal must have negative urine pregnancy test. Pregnancy tests may be completed more frequently as per IRB's/IEC's or as required based upon local regulations.

d. Include Tanner stage assessment at screening for direct enrolling pediatric/adolescent, and at last visit Month 12 for all pediatric/adolescent subjects only. This assessment is not applicable to subjects who participated in study A0081042.

- e. This is a taper medication dispensation only for subjects who will cease treatment with pregabalin. If the subject will continue to receive pregabalin treatment post-study, initiation of taper is at the discretion of the investigator. Subjects who require early discontinuation and require taper, should begin the taper at the time the decision is made to discontinue. These subjects should return approximately 1 week later for follow-up Visit 9.
- f. Assessment of suicidal ideation and behavior:
  - I. MINI-KID only for children and adolescents 6 -<17 years of age at Visit 1B or if they did not have a MINI-KID performed during prior participation to studies referred in Visit 1A.
  - II. C-SSRS "Lifetime" version performed at Visit 1 for all subjects aged 6-65 years who did not have a C-SSRS performed previously. C-SSRS "Since Last Visit" version for all subjects ages 6-65 years for each visit beginning at Visit 2 through Visit 9 or Early Termination.
  - III. Child Behavior Checklist (CBCL) performed for children 4-<6 years of age beginning at Visit 1 and at every subsequent visit until Visit 9 or Early Termination.

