  - Subjects must have had a contrast enhanced computed tomography (CT) or magnetic resonance imaging (MRI) scan of the brain and electroencephalogram (EEG) testing prior to Study A0081041 or Study A0081042. Results must have been consistent with the diagnosis of focal-onset epilepsy and must have demonstrated that no abnormality was likely to be progressive.
5. Male and female subjects 5-65 years of age who have participated in Study A0081105 with a diagnosis of epilepsy (ILAE 2010^3) with PGTC seizures and who continue to satisfy seizure related inclusion criteria for that study (see Protocol A0081105). Subjects who have participated in study A0081105 and who reach the age limit of 66 years of age will still be allowed to enter this study.
6. Currently receiving a stable dose of 1 to 3 antiepileptic drugs at Visit 1. Benzodiazepine medication used on a regular basis will be considered 1 of the concurrent antiepileptic treatments. The vagus nerve stimulator (VNS) is allowed and considered 1 of the 3 antiepileptic treatments.
7. A 12-lead ECG at (the last visit of Studies A0081041, A0081042, A0081105) without significant abnormal findings.

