14. Any subjects considered at risk of suicidal behavior based upon the Columbia Suicidality Rating Scale (C-SSRS) Lifetime (subjects  $\geq 6$  years of age) or Child Behavioral Check List (CBCL)(subjects  $< 6$  years of age) or responses obtained during the Modified International Neuropsychiatric Interview (MINI-KID). A subject should be excluded or a risk assessment should be done by a qualified mental health professional based on responses to assessment of suicidal ideation and behavior and if the subject has had suicidal ideation in the last 6 months prior to screening, suicidal behaviors or attempts in the past year, or current major psychiatric disorders that are not explicitly permitted in the inclusion/exclusion criteria. A risk assessment should also be performed in any child  $< 6$  years of age who has ever exhibited any potentially self-injurious or high-risk behaviors such as hurting himself or herself, or unusual behaviors such as running into traffic or using items as weapons (eg, knife, bat). Any concerns regarding such behaviors should be discussed with the Pfizer clinician prior to study participation or continuation.
15. For subjects who have not participated in Studies A0081041, A0081042, or A0081105 and enrolling directly into Study A0081106, treatment with pregabalin for any reason within 60 days prior to screening, or prior participation in a pregabalin clinical study is prohibited.

16. Known allergy or intolerance to pregabalin or its excipients, including lactose, or other  $\alpha 2\delta$  ligands (eg, gabapentin).
17. Subjects, or subjects whose parents/legally acceptable representatives are investigational site staff members; and subjects, or subjects whose parents/legally acceptable representative are Pfizer employees directly involved in the conduct of the study.

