#### **7.6.3. Columbia-Suicide Severity Rating Scale (C-SSRS)- Subjects 6-65 Years of Age**

The C-SSRS is a prospective semi-structured interview comprised of the following areas of assessment: Ideation, Intensity of Ideation, Behavior and Lethality. It has been used extensively in global clinical studies (academic and industry sponsored) and in a range of therapeutic areas, disorders and indications, including psychiatry, neurology, obesity, urology and endocrinology and is FDA-approved. It has been translated into multiple languages.

The C-SSRS will be used to determine eligibility to enroll at Screening and at every follow-up visit to prospectively monitor suicidal ideation and behavior during the study. If a subject is unwilling or unable to respond, the parent or legally acceptable representative may answer any or all questions based upon their knowledge of the subject and observations of the subject's behavior. Subjects may be interviewed alone or with the parents or legally acceptable representative present based upon discretion of the interviewer.

The C-SSRS will be utilized for all subjects who are 6-65 years of age at Visit 1. The "Lifetime" version will be completed at Screening for those subjects who have not had it administered during participation to study A0081041 or at Visit 1B for direct enrolling subjects. The "Since Last Visit" version of the C-SSRS will be completed at Visits 1A, 2, 3, 4, 5, 6, 7, 8, and 9 or Early Termination. The "Since Last Visit" version will also be completed at any unscheduled clinic visits (ie, clinic visits not included in the [Schedule of Activities](#)). C-SSRS raters must demonstrate successful completion of required training and must have a valid rater training completion certificate in order to perform the assessment.

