#### **7.6.4. Assessment of Suicidal Ideation and Behavior at Screening**

Any subjects considered at risk of suicide based on the C-SSRS Lifetime (subjects 6-65 years of age), or demonstrating at-risk behaviors on the CBCL (subjects 4-<6 years of age) or MINI-KID (6-<17 years of age), or are likely to self harm based on clinical judgment of the investigator, should be excluded from the study or a risk assessment should be done by a qualified mental health professional (MHP – eg, licensed clinical psychologist or psychiatrist; psychiatric nurse practitioner; licensed clinical psychiatric social worker) to determine if the subject is appropriate for study inclusion. A risk assessment should be performed based on responses to suicidal ideation and behavior assessments and if the subject has had suicidal ideation in the last 6 months prior to screening, suicidal behaviors or attempts in the past year, or current major psychiatric disorders that are not explicitly permitted in the inclusion/exclusion criteria. Any positive response on the C-SSRS or a previous history of suicide behaviors should trigger a risk assessment. A risk assessment should be performed in any child <6 years of age who the Investigator has knowledge of him/her exhibiting any potentially self-injurious or high-risk behaviors (eg, hurting himself or herself, running into traffic, or using potential weapons such as knives or bats for self or other injury). A written risk assessment provided by a qualified mental health professional with approval for study participation must be documented prior to subject inclusion for at-risk subjects.

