### **8.3.6. Seizure Frequency**

*Twenty-eight-day seizure rate will be calculated from the seizure diaries and will be reviewed as a means of determining seizure control. Seizure frequency for each seizure type will be summarized using descriptive statistics by visit until the end of the trial by treatment group and overall. No statistical inferences will be performed. PGTC and POS seizure types will be summarized separately.*

**PGTC Seizure Frequency:** will be summarized for subjects from study A0081105 with primary diagnosis of PGTC, and age range from 5 to 65 years. Baseline 28-day seizure rates for PGTC subjects will be the diary data collected prior to initiating double-blind dosing study A0081105. Other than baseline, time points are relative to study A0081106 open-label treatment phase. The 28-day PGTC seizure rate during treatment phase will be reported descriptively for each visit in study A0081106 and overall and will be also reported by age cohorts (5 to 16 years,  $\geq 17$  years). For other types of seizure which are not part of the 28-day PGTC rate (ie, myoclonic, absence seizure, tonic/tonic, clonic, unclassified, status epilepticus) percent of subjects who experienced at least one myoclonic, absence seizure, tonic/tonic, clonic, unclassified, status epilepticus will be summarized.

**POS Seizure Frequency:** will be summarized for subjects from study A0081041, A0081042 and from direct enrollers with primary diagnosis of POS, and age range from 1 month to 16 years. Baseline is not represented for POS subjects as only a subset of these subjects (those from Study A0081041) had seizure diary observations prior to the initiation of study treatment. Baseline seizure data were collected using V-EEG for subjects previously in Study A0081042, which are not comparable to seizure data collected in Study A0081106 using diaries. Direct enrollers into Study A0081106 did not have observation of seizures prior to initiation of study treatment.

The 28-day POS seizure rate during treatment phase will be reported descriptively for each visit in study A0081106 and overall. For other types of seizure which are not part of the 28-day POS rate (ie, unclassified, status epileptic) percent of subjects who experienced at least one unclassified, status epileptic will be summarized.

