### **8.3.9. Suicidal Ideation and Behavior**

#### C-CASA/C-SSRS

The denominator used in the percentages will be the number of subjects assessed for suicidal ideation and behavior (6 to 65 years of age).

The number and percent of subjects within each C-CASA category by treatment group and overall at baseline screening (lifetime) and at any time post-baseline without regard to baseline will be reported.

A subject listing of C-CASA categories as well as the underlying C-SSRS scale data will be presented.

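### Inclusion 5 admits A0081105 subjects who reach 66, but the C-SSRS age band and several SAP labels still stop at 65, so Section 7 assigns these subjects no suicidality scale

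*Protocol*

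**What the plan says.** **Entry.** Protocol 4.1, criterion 5, gives 5 to 65 years for A0081105 subjects and then states that those "who reach the age limit of 66 years of age will still be allowed to enter this study".

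**Places where the C-SSRS stops at 65.**
- Protocol 7.6.3: "The C-SSRS will be utilized for all subjects who are 6-65 years of age at Visit 1".
- Schedule of Activities, footnote f II, gives the Since Last Visit "version for all subjects ages 6-65 years for each visit beginning at Visit 2 through Visit 9 or Early Termination".
- Protocol 7.6.4, on screening, refers to the "C-SSRS Lifetime (subjects 6-65 years of age".
- SAP 6.2.4 repeats the band, and SAP 8.3.9 says: "The denominator used in the percentages will be the number of subjects assessed for suicidal ideation and behavior (6 to 65 years of age".

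**Seizure summary.** SAP 8.3.6 describes the PGTC summary as covering A0081105 subjects "with primary diagnosis of PGTC, and age range from 5 to 65 years".

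**Places with no upper age.** Exclusion 14 covers "Any subjects considered at risk of suicidal behavior based upon the Columbia Suicidality Rating Scale (C-SSRS) Lifetime" and attaches only a lower limit of 6 years to that scale. The procedures for clinic Visits 2 to 9 (Protocol 6.3 to 6.16) list a C-SSRS or CBCL assessment suited to the subject's age. Section 7.6.3 also says that the C-SSRS is used at every follow-up visit.

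**Dosing and taper.** The Protocol Summary says "All eligible adult subjects 17 to 65 years of age will begin dosing of pregabalin". Section 1.3, the dose-adjustment text of Section 3.1 and the adult taper text of Section 3.1 also state 17 to 65. Section 5.1, the starting-dose sentence in Section 3.1 and Table 3 refer to adults without an upper age.

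**The concern.** The entry rule was widened by a year, but the rules that depend on age were not widened with it. Safety and tolerability is the study's only objective, and assessment of suicidal ideation and behavior is one of its named safety endpoints. If a site applies the Section 7 age bands as written, a subject whom the protocol deliberately admits could go through up to eight scheduled post-entry clinic visits (Visits 2 to 9) with no assigned scale. In the SAP, the 65-year labels leave it unclear whether such a subject belongs in the C-SSRS percentages and the PGTC seizure table.

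**Working it through.** The point rests on no sample-size, power or event figure, and the plan gives no number to reproduce. The check sets the age rules side by side.

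1. **Subject aged 66 at Visit 1, entry.** Inclusion 5 admits the subject.

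2. **Same subject, choice of scale.** Protocol 7.6.1 gives the CBCL to ages 4 to under 6. Section 7.6.3 gives the C-SSRS to ages 6 to 65 at Visit 1. At 66 neither applies.

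3. **Whether the visit procedures fill the gap.** They name no upper age, but they ask for the scale that suits the subject's age and point to Section 7 for it. Section 7.6.5 likewise relies on the guidance in earlier sections. The visit text names no lower age either, yet children under 4 fall in neither Section 7 band. So the visit text alone does not settle who is assessed.

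4. **Whether Exclusion 14 fills the gap.** It has no upper age, but it governs eligibility only, and its band differs from that in 7.6.4. It shows the likely intent without assigning a scale during the study.

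5. **Subject aged 65 at Visit 1 who turns 66 on study.** Section 7.6.3 fixes age at Visit 1, so the C-SSRS continues. Footnote f II states the age range for each visit without saying at which date age is taken, so it can be read as no longer applying after the birthday. It contains no stopping rule.

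6. **SAP.** The Safety population is every dosed subject. SAP 6.2.3 computes the PGTC rate for subjects from A0081105, with an open-ended cohort of 17 and older, and Section 8 defines the PGTC cohort by study of origin. Only the label in 8.3.6 stops at 65. Section 8 takes age at randomization in the previous study for age cohorts, but 8.3.9 does not say which age its 6-to-65 label refers to.

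7. **Possible numbers, by assumption only.** The documents give no adult age distribution. Suppose that adults from A0081105 are spread evenly over the 65 − 17 + 1 = 49 one-year bands from 17 to 65, and that 4 to 21 weeks pass between randomization there and entry here. The share aged 66 at entry is then (weeks ÷ 52) ÷ 49:
   - 4 weeks: 0.16%
   - 13 weeks: 0.51%
   - 21 weeks: 0.82%

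   The share aged 65 at entry, to whom step 5 applies, is about 1 ÷ 49 = 2.0%. These are shares of adult roll-overs, not of all subjects, and the true counts may be zero.

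**The case against.** The strongest reply is that this is a labelling slip with no practical effect. The C-SSRS is the only scale in the protocol that could suit a 66-year-old, Section 7.6.3 itself speaks of every follow-up visit, and Exclusion 14 and the visit procedures set no ceiling. A sensible site would use the C-SSRS. This stands as evidence of intent, and it limits the conclusion to a subject who may go unassessed.

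A reader might infer three stronger things, which the documents do not support:
- **That these subjects are treated without suicidality monitoring.** The uncapped texts just named point the other way.
- **That they drop out of the SAP summaries.** The Safety population has no age limit, the PGTC cohort is defined by study of origin, and the C-SSRS denominator is the number assessed, with the ages given as a label. Someone randomized at 65 and entering at 66 is still 65 on the Section 8 cohort basis. Where the SAP does confine out-of-range subjects to listings (CBCL outside 4 to under 6, C-SSRS under 6), it says so; it has no such rule above 65.
- **That all adult dosing and taper text stops at 65.** Section 5.1, Table 3 and one sentence of Section 3.1 do not.

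What remains is that the operative age bands in 7.6.3, 7.6.4 and footnote f II contradict both Inclusion 5 and the protocol's own uncapped text.

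**Conclusion.** The inconsistency is real and of low severity. Taken literally, Section 7 and footnote f II assign no suicidality scale to a subject aged 66 at Visit 1, and 7.6.3 and footnote f II can be read differently for one who turns 66 on study. At worst, a subject could miss up to eight scheduled post-entry assessments. That requires a site to follow the Section 7 band over the visit list, which the documents neither require nor rule out. The number affected is unknown and may be zero; the percentages above rest wholly on the assumed age spread and timing. The target of 100 pediatric completers is not touched. In the SAP the effect is ambiguity over who is counted, not a demonstrated loss of subjects.

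**What to change.** - **Protocol 7.6.3, 7.6.4 and footnote f II, and SAP 6.2.4 and 8.3.9:** replace the 6-to-65 band with 6 years and older, matching Exclusion 14, and state that age is taken at Visit 1. This also removes the difference between 7.6.3 and footnote f II.
- **SAP 8.3.6:** replace the 5-to-65 range with all A0081105 subjects, consistent with SAP 6.2.3 and Section 8.
- **Adult dosing and taper text:** the texts that state 17 to 65 (Protocol Summary, 1.3, 3.1), those with no upper age (5.1, Table 3, one sentence of 3.1) and Inclusion 5 must be reconciled by the sponsor.

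The cost is wording, plus a C-SSRS interview for any subject concerned at visits that are already scheduled.

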#### **4.1.1. Inclusion Criteria for Directly Enrolling Subjects (ie, partial onset seizure subjects who have not participated in either Studies A0081041 or A0081042)**

In order for Direct Enrolling Subjects to be eligible, all of the following inclusion criteria must be met and confirmed prior to, or on, Visit 2:

1. Evidence of a personally signed and dated informed consent document indicating that the parent/legally acceptable representative has been informed of all pertinent aspects

of the study. When there are 2 parents or 2 legally acceptable representatives, consent should be obtained from both of the child's parents/legal representatives if present at the meeting where the informed consent document is signed. Subject to local regulations whenever the minor is able to give assent, the minor's assent must be obtained.

2. Subjects and/or parents/legally acceptable representative who are willing and able to comply with scheduled visits, treatment plan, laboratory tests, and other study procedures.
3. Subjects and/or parent/legally acceptable representative must be considered willing and able to complete daily seizure diaries and monitor seizure frequency.
4. Male and female epilepsy subjects, 1 month (44 weeks gestational age) to 16 years of age inclusive on the date of the Screening Visit with diagnosis of epilepsy with seizures classified as simple partial, complex partial or partial becoming secondarily generalized, according to the International League Against Epilepsy (ILAE 2010^3) (See [Appendix 1](#) for additional seizure types). The diagnosis must be established by:
  - Subject's history (eg, description of seizures excluding confounding disorders such as pseudoseizures, syncope etc.) family history and neurological exam.
  - Subjects must have had a contrast enhanced computed tomography (CT) or magnetic resonance imaging (MRI) scan of the brain within 60 months of the Screening Visit and an EEG within 24 months of the screening visit. However, if clinical symptoms have emerged or a change in a clinical status has occurred such that an imaging study would be required, then a CT with contrast or MRI of the head should be performed regardless of the amount of time that has elapsed since the previous CT/MRI scan. Results must be available as soon as possible following screening and must be completed and reviewed prior to enrollment. Imaging results must be consistent with the diagnosis of focal-onset epilepsy and must demonstrate that no abnormality is likely to be progressive.
  - Subjects must have had an average of at least 3 seizures per month in the 3 months prior to screening.
5. Currently receiving a stable regimen of 1 to 3 antiepileptic treatments (stable within 28 days prior to screening). Benzodiazepine medication used on a regular basis at a stable dosage will be considered 1 of the concurrent antiepileptic treatments. Any PRN benzodiazepine use in addition to AEDs must be discussed with the Pfizer clinician and allowance will be decided on a case-by-case basis. The vagus nerve stimulator (VNS) is allowed and considered 1 of the 3 antiepileptic treatments.
6. A 12-lead ECG at screening without clinically significant abnormal findings as determined by the investigator.

